## **2. Study Objectives**

The primary hypothesis is treatment with vericiguat 10 mg or 15 mg in patients with HFpEF improves physical functioning measured by the KCCQ PLS compared to placebo after 24 weeks of treatment. The secondary hypothesis is treatment with vericiguat 10 mg or 15 mg in patients with HFpEF improves walking distance as measured by the 6MWT compared to placebo after 24 weeks of treatment. The study is designed to have enough power for the primary and secondary hypotheses testing. Other objectives are listed only for descriptive purposes.

Primary objectives:

- To evaluate the efficacy of vericiguat 10 mg in comparison to placebo on improving physical functioning as measured by KCCQ PLS from baseline to week 24.
- To evaluate the efficacy of vericiguat 15 mg in comparison to placebo on improving physical functioning as measured by KCCQ PLS from baseline to week 24.
- To evaluate the safety and tolerability of vericiguat.

Secondary objectives:

- To evaluate the efficacy of vericiguat 10 mg in comparison to placebo on improving distance traveled on a 6MWT from baseline to week 24.
- To evaluate the efficacy of vericiguat 15 mg in comparison to placebo on improving distance traveled on a 6MWT from baseline to week 24.
- To evaluate the efficacy of vericiguat 10 mg in comparison to placebo in increasing the proportion of patients with KCCQ PLS improvement from baseline by >5 points at 24 weeks and other thresholds (e.g. >3, >7, >10, >15, >20), and the proportions with these improvements in the other KCCQ domains OSS, CSS, TSS and SFS.

- To evaluate the efficacy of vericiguat 15 mg in comparison to placebo in increasing the proportion of patients with KCCQ PLS improvement from baseline by >5 points at 24 weeks and other thresholds (e.g. >3, >7, >10, >15, >20), and the proportions with these improvements in the other KCCQ domains OSS, CSS, TSS and SFS.
- To evaluate the efficacy of vericiguat 10 mg in comparison to placebo in decreasing the proportion of patients with KCCQ PLS decline from baseline by >5 points at 24 weeks and the proportions with decline in the other KCCQ domains OSS, CSS, TSS and SFS.
- To evaluate the efficacy of vericiguat 15 mg in comparison to placebo in decreasing the proportion of patients with KCCQ PLS decline from baseline by >5 points at 24 weeks and the proportions with decline in the other KCCQ domains OSS, CSS, TSS and SFS.

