## Stratification

Patients will be randomized within 4 weeks of the screening visit and within up to 6 months after the date of hospitalization for HF or treatment with IV diuretic for HF, and randomization will be stratified according to region and heart rhythm at baseline ECG.

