  modeffects trt01pn*avisitn;
RUN;
```

Based on the responder definitions obtained from anchor-based analysis (Section 4.3.2), a responder is defined as a patient whose improvement from baseline in KCCQ PLS is greater than or equal to responder definition. The number of responders at each visit will be summarized and tested using a chi-square test. Note that missing data will not be imputed in the responder analysis. In addition, the number of patients with KCCQ PLS improvement from baseline by >5 points at 24 weeks and other thresholds (e.g. >3, >7, >10, >15, >20) will be summarized for each arm and assessed using a chi-square test. The number of patients with KCCQ PLS decline from baseline by >5 points and other thresholds (>3, >7, >10, >15, >20) at 24 weeks will be summarized by each arm and examined using a chi-square test as well. Further, PDF and CDF of change from baseline at 24 weeks for KCCQ PLS domain will be plotted to compare the proportion of patients who are meeting certain threshold from vericiguat and placebo arms. The Kolmogorov–Smirnov test will be performed to determine if the curves are significantly different.

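### KCCQ PLS improvement and decline proportions are compared by unadjusted chi-square; adjusting for baseline PLS and the stratification factors would recover precision at almost no cost

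*SAP*

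**What the plan says.** SAP 6.2.3.1 plans three sets of comparisons of PLS proportions.

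- Anchor-based responders: "The number of responders at each visit will be summarized and tested using a chi-square test".
- Improvement beyond fixed thresholds (>5, and others from >3 to >20) at week 24: the counts "will be summarized for each arm and assessed using a chi-square test".
- Decline beyond the same thresholds: the counts "at 24 weeks will be summarized by each arm and examined using a chi-square test as well".

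No covariate or stratum is named for any of them. For the responder analysis the SAP adds: "Note that missing data will not be imputed in the responder analysis". We found no adjusted or stratified analysis of these proportions in either document.

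The same section fits the primary MMRM with baseline PLS, region and heart rhythm. SAP section 3 states that "randomization will be stratified according to region and heart rhythm at baseline ECG".

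The status of the proportions is mixed. SAP section 2 and Protocol section 4 list improvement ("proportion of patients with KCCQ PLS improvement from baseline by >5 points at 24 weeks and other thresholds") and decline ("proportion of patients with KCCQ PLS decline from baseline by >5 points at 24 weeks") under secondary objectives. Protocol 9.4 puts the proportions among the exploratory efficacy variables, and SAP 4.3.2.1 calls the responder analysis exploratory. Protocol 10.3.1 promises nominal p-values for the anchor-based responders. The multiplicity scheme in SAP 6.2.5 covers only the mean PLS change and the 6MWT.

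**The concern.** Baseline predicts whether a patient can cross a change threshold. PLS is bounded at 100 (Protocol 9.4.1) and the entry criteria set no upper PLS limit. With all six items answered the score moves in steps of 100/24 = 4.17 points, so a change of >5 needs two steps (8.33) and a change of >20 needs five (20.83). A patient starting at 95.8 or 100 cannot improve by >5, and one starting at 83.3 or above cannot improve by >20. An unadjusted test leaves this known variation in the error.

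The SAP recognises the ceiling elsewhere. The PEAS excludes patients with no limitation at baseline, and there is a subgroup with baseline PLS of 75 or more. But the PEAS repeat applies to the primary model, not to the responder tests.

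At stake is how clearly the proportions can help interpret a mean PLS difference. The thresholds were developed for that purpose (SAP 4.3.2), alongside the established between-group thresholds and the distribution plots.

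**Working it through.** **Inputs from the documents** (Protocol 10.4): 245 per arm, difference 5 points, SD 21, negligible dropout.

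**Assumptions not in the documents:** SD 21 is read as the SD of change; placebo mean change is +5; baseline mean is 55 to 65 and baseline SD about 20 to 28; r is varied. Responder power is at two-sided 0.05.

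**1. The plan's own power.** SE = 21·√(2/245) = 1.897. Power for one dose at two-sided 0.025 = Φ(5/1.897 − 2.241) = Φ(0.394) = 65.3% (stated 65%). With correlation 0.5 from the shared placebo arm, power for at least one dose is 80.6% (stated 80%). The documents state no power for any proportion.

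**2. Chi-square power, normal change.**
- Improvement >5: placebo P(change > 5) = 50.0%; active Φ(5/21) = 59.4%. Pooled proportion 0.547. Power = Φ[(0.0941 − 1.96·√(2·0.547·0.453/245)) / √((0.2500 + 0.2411)/245)] = Φ[(0.0941 − 0.0882)/0.0448] = 55.3%.
- Decline >5: Φ(−10/21) = 31.7% against Φ(−15/21) = 23.8%; power 50.2%.

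**3. Effect of adjustment by r.** Simulated power, chi-square → logistic regression with treatment, baseline PLS, region and rhythm; unbounded score, with strata explaining no variance:

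| r | Improvement >5 | Decline >5 |
|---|---|---|
| 0 | 56% → 55% | not tabulated |
| −0.2 | 55% → 55% | not tabulated |
| −0.3 | 56% → 59% | 51% → 53% |
| −0.4 | 56% → 60% | 49% → 53% |
| −0.5 | 57% → 62% | 51% → 57% |
| −0.6 | 57% → 67% | 50% → 60% |

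If the strata explain 3% of variance, the gain reaches about 8 points at r = −0.5 and 11 to 13 at r = −0.6. At |r| of 0.3 to 0.5, decline >15 gains 1 to 3 points and decline >20 gains 0 to 2.

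**4. Which r is plausible.** If baseline and week-24 SDs are equal, cov(baseline, change) = −var(change)/2, so r = −SD(change)/(2·SD(baseline)). With SD(change) = 21, baseline SDs of 20, 24 and 28 give r = −0.53, −0.44 and −0.38. An |r| below 0.3 would need a baseline SD above 21/0.6 = 35 on a 0–100 scale.

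**5. Bounded 24-step score.** Baseline mean 60, adjusting for baseline only, 1,500 trials per scenario. Improvement >5, chi-square against logistic:
- baseline SD 20: 54% vs 63%
- baseline SD 22: 54% vs 61%
- baseline SD 24: 51% vs 58%
- baseline SD 28: 45% vs 52%

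The gain was 6 to 8 points at ≥12.5 and 5 to 9 at >20. Decline gained about 1 to 5 points in most runs. At decline >5 some runs reached 6 or 7, for example 49.6% → 55.4% with r = −0.5. With r = −0.3 on a bounded score, improvement >5 gained about 2 to 4 points and decline >5 about 1 to 3.

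**6. Validity.** Under the null, rejection rates were 5.4% (chi-square) and 4.8% (adjusted) in one set of runs and 4.6% and 4.9% in another. All are near 5%.

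**The case against.** The strongest reply is that this is an efficiency preference about secondary-to-exploratory tests. An unadjusted comparison of observed proportions is transparent, standard and valid. There are many such comparisons (several thresholds, two directions, several visits, two doses), none has a power target, and no success claim depends on any of them. SAP section 2 defines the hypotheses the study is powered for as mean PLS and 6MWT. All of this stands, and it limits the weight of the point.

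It is also fair that the size rests on a correlation the documents never state, and that a conditional odds ratio answers a different question from a difference in proportions. The first is met by giving the range, the second by reporting a standardised difference.

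Three stronger readings are tempting:

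- A reader might infer that a confirmatory secondary claim is at risk because the proportions appear under secondary objectives. They sit outside the gatekeeping and are elsewhere called exploratory, so the documents do not support that.
- A reader might infer that ignoring the strata, or including patients at the ceiling, makes the test invalid. Its simulated type I error is near 5%, and randomisation spreads ceiling patients across the arms.
- A reader might apply the 4 to 10 points to decline as well. The calculations do not support that.

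**Conclusion.** The point holds as a loss of precision. The SAP leaves out of these comparisons a strong predictor and two stratification factors that it already uses for the mean of the same score.

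With 245 per arm, change SD 21, effect 5 and placebo change +5, adjustment is worth about 4 to 10 points of power for improvement thresholds if r is about −0.4 to −0.55, which corresponds to a baseline SD of about 20 to 28. It is worth about 0 to 3 points if |r| is 0.3 or less, and 10 to 13 at 0.6. For decline, about 1 to 5 points is typical, with 0 to 3 at the highest thresholds when |r| is moderate. Baseline SD, placebo change and r are assumptions. Missing week-24 scores would lower the power of both tests, because these analyses use observed cases.

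This should be changed because it is cheap. It does not threaten the primary or 6MWT conclusions.

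**What to change.** Before unblinding, amend SAP 6.2.3.1 as follows.

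1. For each dose versus placebo, make the inferential comparison of improvement, decline and anchor-based responder proportions a logistic regression on treatment, baseline PLS, region and heart rhythm.
2. Report the standardised (marginal) difference in proportions with its 95% CI, and take the p-value from that same standardised estimate so that interval and test cannot disagree.
3. Keep the crude counts and the chi-square result beside it, labelled descriptive.
4. State that the p-values are nominal, and give the proportions one status across SAP section 2, SAP 4.3.2.1 and Protocol 9.4.

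The cost is SAP wording and brief programming. All covariates are already collected, and no new data are needed. The change should be made before unblinding, because adjustment added afterwards would look post hoc.

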#### **4.3.2.1 Updates from FDA Type C meeting**

The proposed KCCQ-PLS thresholds for meaningful within-patient changes determined during the interim and blinded dataset analysis of 8.33 and 12.5 for improvement and -4.17 for worsening will be added to the pre-specified thresholds (e.g. >3, >7, >10, >15, >20) for exploratory responder analysis already included in the SAP version 1.0. Following an FDA request made during the Type C meeting held on 6th November 2019, the anchor-based analysis will be additionally run on the full trial dataset prior to unblinding to further inform interpretation of the primary endpoint of KCCQ-PLS change from baseline to week 24.

Supportive analyses, including distributional-based approaches, receiver-operating characteristic curves and non-parametric discriminant methods will not be re-evaluated on the full trial dataset prior to unblinding.

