#### **6.2.3 Primary efficacy variable**

##### **6.2.3.1 Primary Analysis of the Primary Efficacy Variable**

The primary endpoint will be change in KCCQ PLS from baseline to week 24.

The estimand of interest is the de facto or treatment policy estimand.

Population: Defined through study inclusion/exclusion criteria (see protocol Section 6.1 and 6.2).

Variable: Change from baseline in KCCQ PLS from baseline to Week 24.

Approach of intervention effect: Regardless of stopping study treatment or adherence to study treatment.

Summary measure: Difference of LS means at Week 24.

The primary analysis will be performed on the FAS (KCCQ) (Section 5.1.2). Missing data will be imputed based on a pattern-mixture model with control-based pattern imputation (Appendix 9.1). The main idea of this method was introduced by Little and Yau (1996) [20] and later refined by Ratitch and O'Kelly (2011) [21]. In this control-based pattern imputation, PROC MI is called in such a way that it builds its imputation model only on data from the control arm, while it imputes missing data in both control and experimental treatment arms using a single control-based imputation model. In other words, the methods will be implemented using copy reference approach. For those patients who had died during the study, they will be imputed with the worst case outcome, i.e., a zero score from the time of death onward.

The analysis of each imputed dataset will be performed using mixed-effects model for repeated measures (MMRM), including treatment, region, heart rhythm, study visit as fixed effects, interaction between study visit and treatment group, and adjustment for the baseline PLS values as covariates. The model will assume an unstructured covariance matrix for within-patient variability.

The model statement is:

$$Y_{ijklm} = \mu + \beta x_i + t_k + r_l + h_m + v_j + (tv)_{jk} + \varepsilon_{ij}$$

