### 6.2.4 Secondary efficacy variable

The secondary endpoint is change from baseline in the 6 MWT at 24 weeks. The estimand of interest is the de facto or treatment policy estimand.

Population: Defined through study inclusion/exclusion criteria (see protocol Section 6.1 and 6.2).

Variable: Change from baseline in 6 MWT from baseline to Week 24.

Approach of intervention effect: Regardless of stopping study treatment or adherence to study treatment.

Summary measure: Difference of LS means at Week 24.

[figure not shown]
The secondary endpoint will be analyzed in the same manner as the primary endpoint and on the KCCQ (6MWT) (Section 5.1.3). Missing data will be imputed based on a pattern-mixture model with control-based pattern imputation (Appendix 9.1). For those patients who had died during the study, a score of 0 will be assumed from the time of death onward.

A supportive analysis will be repeated using the MMRM model without any missing data imputations. Also, the same model will be applied to all assessments post-baseline prior to study treatment termination.

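### The -4.17 worsening cut-off misses every one-step decline on a complete PLS form unless change is rounded, and the threshold counts have no stated rule for deaths

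*SAP*

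**What the plan says.** SAP 4.3.2.1 reports the thresholds from the blinded anchor-based analysis: "8.33 and 12.5 for improvement and -4.17 for worsening will be added to the pre-specified thresholds". It describes that list as being "for exploratory responder analysis already included in the SAP version 1.0".

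SAP 6.2.3.1 gives the rule for improvement: "a responder is defined as a patient whose improvement from baseline in KCCQ PLS is greater than or equal to responder definition". It follows this with "Note that missing data will not be imputed in the responder analysis". It then adds counts of improvement by more than 5 points and at other thresholds, and the matching decline counts: "The number of patients with KCCQ PLS decline from baseline by >5 points and other thresholds". It states no operator for the -4.17 cut-off, no rounding rule, no denominator and no rule for deaths in these counts.

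For the primary analysis the same section says of patients who died that "they will be imputed with the worst case outcome, i.e., a zero score from the time of death onward". SAP 6.2.4 does likewise for the walk test: "For those patients who had died during the study, a score of 0 will be assumed from the time of death onward".

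SAP 2 lists among the secondary objectives the efficacy of each dose "in decreasing the proportion of patients with KCCQ PLS decline from baseline by >5 points at 24 weeks".

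**The concern.** There are two gaps in how the threshold counts are specified.

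(a) **Cut-off.** The three anchor-derived values look like one, two and three item steps printed to two decimals. Rounding 8.33 down is harmless. Rounding 4.17 up puts the cut-off just beyond the step it is meant to capture. Two programmers following the SAP could then report clearly different percentages worsened.

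(b) **Deaths.** The SAP itself calls the zero score at death an imputation. If the responder analysis imputes nothing, a patient who dies before the visit has the worst outcome in the primary analysis but is never a decline in the counts. At stake is how the PLS result is interpreted, which is what these thresholds are for.

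**Working it through.** **Inputs.** Six equally weighted items with five scored levels, rescaled to 0-100 (Protocol 9.4.1, Table 9-3). At least 3 of 6 items needed (SAP 4.2). Cut-offs -4.17, 8.33 and 12.5 (SAP 4.3.2.1). SD 21, a 5-point effect and 245 per arm (Protocol 10.4). Mean changes and death rates are not in the documents and are assumed below.

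**Step size.** With k items answered, PLS = 100 x (item mean - 1)/4, so one step in one item is 100/(4k):

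- k = 6: 4.1667
- k = 5: 5.00
- k = 4: 6.25
- k = 3: 8.33

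**Reproducing the SAP's thresholds.** On a complete form one, two and three steps are 100/24 = 4.1667, 200/24 = 8.3333 and 300/24 = 12.5. To two decimals these are 4.17, 8.33 and 12.5, as in SAP 4.3.2.1.

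**Enumeration.** A complete form has 25 possible scores, hence 24 one-step, 23 two-step and 22 three-step changes. Number meeting each cut-off with >=, computed in double precision:

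| Handling | one step, 4.17 | two steps, 8.33 | three steps, 12.5 |
|---|---|---|---|
| Unrounded change | 0 of 24 | 23 of 23 | 19 of 22 |
| Change rounded once to 2 decimals | 24 of 24 | 23 of 23 | 22 of 22 |
| Scores stored to 2 decimals, then subtracted | 16 of 24 | 23 of 23 | 22 of 22 |

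The 19 of 22 is floating-point error at an exact tie. With > instead of >=, one-step declines are counted 0 of 24 times even after rounding change to two decimals.

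On unrounded change the -4.17 cut-off needs two steps (8.33) on a complete form. It is then the same count as decline >5 and decline >7, which also need two steps. With 3, 4 or 5 items answered at both visits a one-step decline is 5.00 or more and is counted, so the cut-off means different things on different forms.

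**How many patients this moves.** Assume change is normal with mean m and SD 21 and all forms are complete. With s = 100/24, the share exactly one step down is Phi((-0.5s - m)/21) - Phi((-1.5s - m)/21):

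- m = 0: 7.7% (about 19 of 245)
- m = 5: Phi(-0.337) - Phi(-0.536) = 36.8% - 29.6% = 7.2% (about 18 of 245)
- m = 10: 6.3% (about 15 of 245)

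For a 5-point effect, the between-arm difference in percentage worsened moves by the difference of these shares: 0.6 points for means 0 v 5, and 0.9 points for means 5 v 10.

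**Deaths (rates assumed).** Take 245 per arm, with deaths counted as declines.

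- One arm, 3% deaths and about 20% decline among survivors: 48/238 = 20.2% becomes 55/245 = 22.4%.
- Between arms, 20% decline among survivors in both: the share is 0.20(1 - d) + d. With deaths 2% v 2% the difference stays 0.0. With 5% v 2% it becomes 24.0% - 21.6% = 2.4 points, with SE sqrt(0.24 x 0.76/245 + 0.216 x 0.784/245) = 3.8 points.

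**The case against.** Several stronger readings are tempting, and the documents do not support them.

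- *The operator at +12.5 is open, because the value joins a list written with >.* It is not. SAP 6.2.3.1 applies >= to the definitions from the anchor-based analysis, and 8.33 and 12.5 are those definitions. Only worsening lacks an operator.
- *The decline counts are expressly observed-case.* This is an inference. The no-imputation note precedes the threshold counts and names only the responder analysis. The link is SAP 4.3.2.1, which places the listed thresholds in the responder analysis, and that list does not name >5. Still, no other death rule is given for these counts.
- *A secondary endpoint is compromised.* SAP 2 treats objectives beyond the PLS and 6MWT hypotheses as descriptive, and Protocol 9.4 puts the proportions among exploratory variables.
- *Up to a tenth of patients are affected.* That needs an SD near 15, which the documents do not give.

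Three further points for the plan are fair. SAP 6.2.1 defers scoring to instructions that are not in the documents, and these may fix score precision. The likely intent of -4.17 is plainly one step. SAP 6.2.9 reports deaths separately and includes a composite of CV death with KCCQ CSS worsening, among other components. All this keeps the point small. It does not supply the missing comparison rule for worsening or the missing death rule.

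**Conclusion.** The point holds as a minor specification gap. Taken literally on unrounded scores, -4.17 gives a wrong count: it misses all 24 one-step declines on a complete form and there repeats two existing decline counts. At the planned SD of 21 this concerns 6.3% to 7.7% of patients and moves the between-arm difference by 0.6 to 0.9 points, assuming normal change, mean 0 to 10 and complete forms. PLS is bounded, so normality is an approximation.

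The death part rests on the natural reading of the no-imputation note. Its size depends on death rates that the documents do not give. It is likely small: even the assumed 5% v 2% imbalance moves the decline difference by less than one standard error. Deaths before any post-baseline PLS are outside FAS (KCCQ), hence outside the primary analysis as well. The primary test, the 6MWT test and power are unaffected.

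**What to change.** Add to SAP 6.2.3.1 before unblinding:

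1. Define worsening as a decline of at least one item step (100/24). Compute change from unrounded scores, round it once to two decimals, and count decline >= 4.17. Use the same rounding for the >= 8.33 and >= 12.5 improvement counts so that exact steps are not lost to floating-point error. If only two-decimal scores exist, use decline >= 4.15. This captures all 24 one-step declines and no smaller change, because over all forms with 3 to 6 items answered the achievable changes next to 4.1667 are 3.75 and 5.00. A literal 0.01 tolerance (>= 4.16) catches only 17 of 24 in double precision.
2. For FAS (KCCQ) patients dead by the scheduled visit date with no PLS in the window, set PLS to 0 as in the primary analysis and apply each threshold to the resulting change. If every death is instead to count as worsened at every threshold, say that this is a composite rule. It differs from the zero score when baseline is low: a baseline of 20 gives a decline of 20, which is not >20. Survivors stay observed-case. The denominator is patients with an evaluable PLS at the visit or dead by it.
3. Apply the same death rule to the PDF/CDF comparison and to the other KCCQ threshold counts in SAP 6.2.6, or label those as observed cases.

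The cost is a few sentences and minor programming, with no new data. Under the death rule, response percentages fall slightly and decline percentages rise slightly.
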